7.9.1.3 Sample size justification

The sample size justification for the primary objective is provided in section 6.

7.9.1.4 Analysis methods

The primary analysis will use the CC set as described in section 7.1.3. TEED is determined by the stimulation parameters (e.g., pulse width, frequency, amplitude) and the measured impedance.

The calculation of TEED when using constant voltage is:

$$\text{TEED} = \text{voltage}^2 \times \text{frequency} \times \text{pulse width} / \text{impedance}$$

The calculation of TEED when using constant current is:

$$\text{TEED} = \text{current}^2 \times \text{frequency} \times \text{pulse width} \times \text{impedance}$$

The previous formulas can be used without modification with DBS lead models 3387 or 3389. When the lead is the SenSight™ system and it is programmed in Directional Stim Mode or Ring Mode Stimulation, each contact is considered independent. For each segment that is activated, TEED will be calculated individually using the formulas above, and then summed to obtain the total TEED for the lead. Leads programmed with monopolar settings will use the electrode unipolar impedance between the case and the active electrode. If 2 cathodes are used (dual monopolar settings), TEED will be calculated for each contact separately, and total TEED will be determined for the lead as the sum of the two TEED. Leads programmed to bipolar will use the impedance between the active electrodes.

Directional Stim Mode may be programmed during the follow-up phase. The primary endpoint on the difference in TEED will be assessed by means paired t-test to compare the difference in TEED for aDBS (preferred mode, single or dual threshold) to cDBS. Normality of the outcome will be assessed with the Shapiro-Wilk test. If large violations to the normality assumption are observed ($p < 0.05$), the primary analysis will use a Wilcoxon signed-rank test to assess statistical significance. To compute TEED using the formula above, the average current drain from the JSON session data will be computed using the average stimulation currents from the timeline feature in the 14 days prior to the visit. This will be computed as the average of the currents from the timeline feature using the epochs that align with the analysis set (e.g., As-Treated analysis set uses the actual aDBS mode as reported from the device). The pulse-width, frequency, and impedance will be determined from the JSON session data as per study procedure. TEED calculation will be provided by Rune Labs.

7.9.1.5 Supporting analyses

In order to demonstrate the decreased TEED during adaptive (aDBS) as compared to continuous DBS (cDBS), using a within-subject comparison in this crossover design, it is necessary to test for period effects (where the treatment effect is dependent upon which treatment was applied first) and carryover effects (where the treatment effect from the first crossover period affects the response during the second period). The average TEED will be analyzed using a general linear model appropriate for a two-treatment, two-period crossover design to inspect the period effect and carry-over effect. A significance level of 0.15 will be applied to the analysis of period effect and carry-over effect to allow for a more conservative analysis. Should any significant period or carryover effects be detected, data from the first crossover period may be compared between randomized groups in a parallel-design fashion.

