9.8.1. Period A initiation /Visit1

Same as Randomization day.

The PI/ Sub investigator should confirm the subject is in cDBS.

The following data will be collected:

- Concomitant medications (non-PD)
- PD medications
- Programming session upload, with device interrogation and BrainSense data included in the JSON session data report
- PDQ-39 (subject's assessment of cDBS or aDBS washout period)
- EQ-5D-5L
- MDS-UPDRS II ("best" conditions)
- MDS-UPDRS II ("worst" conditions)
- MDS-UPDRS III (On stim (cDBS)/On med) – trained rater
- MDS-UPDRS IV – trained rater
- UDysRS (subject's assessment of cDBS or aDBS washout period)
- Upload data collected from Apple Watch, including movement and sleep data (Operation confirmation)
- AE and device deficiency assessment (As they occur)
- Protocol Deviations (As they occur)

At the end of the visit, the PI/Sub investigator should program the subject to the assigned DBS mode for Period A. Start the program for Period A, and return the subject home.

Subjects will participate in a data collection of movement, sleep data and dosing cycle of PD medications with Apple Watch and iPhone. The subject will be given an Apple Watch and linked iPhone and instructed on its use. Upon receipt, the subjects should put on and activate the Apple Watch. Data collection will start immediately and will continue as long as the subject is wearing the watch and the watch is charged. After the recording, the subject will upload the data collected from Apple Watch via iPhone to the database specified by Rune Labs, Inc. Subjects will also record their PD medications in an iPhone application (STRIVE App, Rune Labs) every 14 days during Period A and Period B in aDBS treatment phase. An Apple Watch calendar will be set up to get notifications from Apple Watch for medication log. Subjects will receive further guidance on the daily charging schedule of the Apple Watch and data upload through the iPhone application (STRIVE App, Rune Labs, Inc.). Detailed procedures for the Apple Watch/iPhone data collection are outlined in the Rune Labs Study Manual. In principle, the data collected from an iPhone will be used for Data of PD medication cycle, but if the data is missing, the data recorded in a medication diary etc. can substitute by reporting in CRFs.

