12.4.1. Supporting analyses

The analysis approach makes two main assumptions: no period effect and no carryover effect (including their interaction). These assumptions will be tested first. If the period and carryover effects is not significant (i.e. the p-value is greater than or equal to 0.10), then the data from the two periods can be combined and analyzed. Otherwise, the data only from period A can be used to estimate the treatment effect. Details on supporting analyses will be reported in the statistical analysis plan.

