MDS-UPDRS IV				X		X		X	X	X	X	
DBS GIC						X		X				
Preference questionnaire		X ¹						X ⁵				
Satisfaction questionnaire								X ⁵			X	
Apple Watch/iPhone distribution and programming				X								
Apple Watch/iPhone data collection				X	X ²	X	X ²	X	X	X	X	
Device data		X ³		X		X		X	X	X	X	
Event markers (Option)					X		X		X	X	X	
Adverse Events	As they occur											
Device Deficiencies	As they occur											
Protocol Deviations	As they occur											

Visit	Enrollment	Baseline	Randomization	aDBS Treatment Phase					Follow-up phase			Exit
				Visit 1	Out of clinic	Visit 2	Out of clinic	Visit 3	Visit 4	Visit 5	Visit 6	
Visit ranges (From the previous visit)		Up to 30 days		Up to 30 days		45 days ⁴		45 days ⁴	45- 60 days ⁴	45- 60 days ⁴	45- 60 days ⁴	
Reason for exit												X

¹ Not required if data collected prior to Early Adapter Part II

² PD Medication cycle, every 14 days during 45 days of Period A and B; Calendar reminders set on Apple Watch, with instructions

³ If Signal test was implemented

⁴ Visit ranges ± 7 days

⁵ Perform before unblinding subjects

⁶ Perform after unblinding subjects

6. Determination of Sample Size

Based on the registry data and the bench testing, when a conservative estimate for the first quartile of TEED data for initial devices in the registry is used, TEED is expected to decrease between 35 and 22 units for aDBS single threshold mode and aDBS dual threshold mode, respectively ^{1,2}. A standard deviation of 36 results in a medium to large effect size of 0.7858. Based on these assumptions, the sample size was estimated using a two-sided ($\alpha=0.05$) paired T-Test means (PASS 2019) to compare the difference in aDBS TEED to cDBS TEED of 28 and a standard deviation of 36, a minimum of 20 subjects achieves at least 90% power for the detection of an effect size of 0.78. It is anticipated that around 25% of subjects will have unilateral DBS and so they will be excluded from the primary analysis. Considering this information, it is estimated that between 20-30 subjects implanted with a commercially available Medtronic DBS system with Percept PC INS will be enrolled to obtain a study population of 20 (bilateral DBS).

7. Statistical Methods

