7.11 Changes to Planned Analysis

Any change to the data analysis methods described in the SAP will require an amendment only if it changes a principal feature of the SAP. Any other change to the data analysis methods described in the SAP, and the justification for making the change, will be described in the clinical study report.

8. Validation Requirements

All collected data will be reviewed for completeness correctness and consistency. In case of issues, queries will be sent to the investigator to complete, correct or comment the data. Statistical programming code that affects the result of the main analysis (e.g., not including sensitivity or supporting analyses) for the primary objective shall be validated using Level I validation. Programming code for randomization and programming code that affects the result of the main analysis for the secondary objective(s) shall be validated using at least Level II validation. In addition, those main statistical analyses that are planned for publication and have not been previously validated should be validated using at least Level II validation. The CIP deviation summary shall be validated using at least Level III validation and the high-level adverse event summary shall be validated using at least Level II validation. Additional measures where a p-value or confidence interval has been generated may need to be validated using at least Level II validation.

9. References

1. Simon Little, MA, MBBS, [name], Spencer Neal, BEng (Hons), Baltazar Zavala, BA, [name], [name], et al. Adaptive Deep Brain Stimulation in Advanced Parkinson Disease. Little et al. 2013;74(3):449-457.
2. Simon Little, Martijn Beudel, Ludvic Zrinzo, Thomas Foltynie, Patricia Limousin, Marwan Hariz, et al. Bilateral adaptive deep brain stimulation is effective in Parkinson's disease. Neurosurg Psychiatry 2016;87:717-721. Epub;2015
3. CONSORT 2010 statement: extension to randomised crossover trials. BMJ 2019; 366:l4378

10. Appendix A

For each subject, two weeks prior to each adjustment visit will be used for this analysis. Data will be provided for aDBS treatment phase 1 and follow-up phase. The following data from JSON, BrainSense and Apple Watch will be provided from Rune Labs.

Source	Parameter	Value/ Category	Description
OC	ID	XXX	the patient ID will be as from OC
	Phase	1/2	1= aDBS treatment phase 2 = follow-up phase
	Next Visit	1/2/3/4/5/6	
Percept data	Group	A/B/C/D	
	N hours available within 2 weeks prior to the visit	Number	

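### Any Period A-only estimate of the TEED difference should be prespecified as an ANCOVA on Visit 1 cDBS TEED; neither document names a baseline adjustment for it

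*SAP*

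**What the plan says.** The main analysis of TEED is a paired comparison within subjects (protocol 12.4, SAP 7.9.1.4). Both documents then test for period and carryover effects and allow a fallback to the first period.

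- Protocol 12.4.1 combines the two periods if "the p-value is greater than or equal to 0.10". It continues: "Otherwise, the data only from period A can be used to estimate the treatment effect". Details are deferred to the SAP.
- SAP 7.9.1.5 states that "A significance level of 0.15 will be applied to the analysis of period effect and carry-over effect". If either is significant, "data from the first crossover period may be compared between randomized groups in a parallel-design fashion".

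Neither section names an estimator, a covariate or a change score for the first-period comparison, and neither gives its power.

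The trial does collect what a baseline needs. Before Period A starts, protocol 9.8.1 requires that "The PI/ Sub investigator should confirm the subject is in cDBS", and it lists a device interrogation with BrainSense data among the Visit 1 uploads. Protocol 12.4 and SAP 7.9.1.4 compute TEED from that kind of session data: average current over the 14 days before the visit, pulse width, frequency and impedance. SAP Appendix A lists TEED as a parameter and includes 1 among the visit codes.

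**The concern.** The paired test makes each subject their own control, so it needs no baseline covariate. A Period A-only comparison gives that up. It sets aDBS in one half of the sample against cDBS in the other, and the spread of TEED between subjects enters the standard error in full.

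TEED is calculated from each subject's own settings and impedance, and inclusion criterion 6 asks for stable cDBS parameters. Visit 1 cDBS TEED is therefore a plausible predictor of Period A TEED, particularly in subjects who stay on cDBS in Period A. No planned analysis uses it as a covariate.

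Two things are at stake: a Period A estimate less precise than the data allow, and a choice of adjustment left until about 20 subjects' results are visible, when any choice is open to challenge.

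**Working it through.** **Inputs.** Difference 22 and SD of the paired difference 28 (protocol 12.8), or 28 and 36 (SAP section 6). Two-sided alpha 0.05, as in both of those sections. 20 completers (protocol section 5). Permuted blocks with no stated ratio (protocol 9.7), so 1:1 and 10 per group are assumed.

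**The plan's own figure.** Paired t-test, n = 20, 19 df. Noncentrality is 22/28 × √20 = 3.51, giving power 91.5%. With 28/36 it is 91.0%. In both cases 20 is the smallest n that reaches 90%, so the stated sample size reproduces.

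**Between-subject SD.** This is not given. With equal variances in the two modes and within-subject correlation ρ, the SD per mode is σ = 28/√(2(1−ρ)). ρ is an assumption and is varied.

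**Unadjusted Period A comparison.** Noncentrality = (22/σ) × √(10/2), 18 df.

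**ANCOVA on Visit 1 cDBS TEED, one common correlation.** Residual SD = σ√(1−ρ²). Noncentrality = 22/(σ√(1−ρ²)) × √5 × √(1−1/18), 17 df. The last factor allows for chance baseline imbalance.

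| ρ | σ | Unadjusted power | ANCOVA power |
|---|---|---|---|
| 0 | 19.8 | 65% | 62% |
| 0.3 | 23.7 | 50% | 52% |
| 0.5 | 28.0 | 38% | 46% |
| 0.7 | 36.1 | 25% | 42% |
| 0.8 | 44.3 | 18% | 40% |
| 0.9 | 62.6 | 12% | 38% |

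The SAP inputs give the same pattern: 38% against 45% at ρ = 0.5, 25% against 41% at 0.7, and 11% against 37% at 0.9.

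**Separate correlations.** Visit 1 is on cDBS, so its correlation r with Period A cDBS may exceed its correlation ρ with Period A aDBS. By simulation (20,000 trials per setting, inputs 22/28), ANCOVA power at r = 0.95 is 65% for ρ = 0.5, 60% for 0.7 and 47% for 0.9. At r = 0.8 it is 57% for ρ = 0.5 and 47% for 0.7. The highest value in any setting examined was 74% (ρ = 0, r = 0.95).

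**Sidedness.** SAP 7.9.1.2 states a one-sided alternative with a 0.05 threshold. At one-sided 0.05 the unadjusted power is 77%, 52%, 37% and 19% at ρ = 0, 0.5, 0.7 and 0.9, against 96% for the paired test. The relative loss is similar.

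**How often the route opens.** If the two pretests were independent and neither effect existed, at least one would be significant with probability 1 − 0.85² = 27.8% at the SAP's level, or 1 − 0.90² = 19% at the protocol's.

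**The case against.** The strongest counter-argument is that this analysis is optional. SAP 7.9.1.4 fixes the primary analysis as the paired test, while the first-period comparison sits under supporting analyses with permissive wording. If it is only supportive, the paired test still carries the conclusion. That stands for the SAP. Protocol 12.4.1 reads more like a substitution for the combined analysis, but it too is permissive. A reader might infer that the Period A result will replace the crossover result; the documents allow that reading without committing to it.

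Other stronger readings are also unsupported:

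- *The plan chooses unadjusted TEED.* It does not. It is silent and does not rule out adjustment.
- *Between-subject variation swamps the effect.* This cannot be shown without a between-subject SD. On the derivation above, σ exceeds 22 only when ρ is above about 0.19, since 1 − (28/22)²/2 = 0.19.
- *Chance imbalance biases the estimate.* Under randomisation it is sampling variance, already counted in the power figures, although it can displace the estimate in the one trial that is run.
- *Adjustment removes most of the between-subject variance.* The fraction removed is ρ², which passes one half only above about 0.71.

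The practical objection has force. SAP Appendix A uses "For each subject, two weeks prior to each adjustment visit will be used for this analysis", but its phase codes cover only the treatment and follow-up phases, so delivery of the window before Visit 1 is unclear. The washout may last only 7 days (protocol 9.6) against a 14-day TEED window, so that window can include aDBS. Baseline may also fall on the same day as Visit 1 (end of protocol 9.6). The covariate is therefore derivable but not ready-made.

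**Conclusion.** The point holds as an omission with a clear remedy. A Period A-only estimate is permitted and no baseline adjustment is specified for it. On the protocol's inputs, its unadjusted two-sided power is at most about 65% for any non-negative ρ and falls to between 38% and 12% for ρ from 0.5 to 0.9, against 91% for the paired test. ANCOVA on Visit 1 cDBS TEED recovers about 8, 16 and 26 percentage points at ρ = 0.5, 0.7 and 0.9 under one common correlation, and more if Visit 1 cDBS tracks Period A cDBS closely. Under one common correlation the gain is about 1 point at ρ = 0.3, and at zero there is a loss of about 3 points. Adjustment does not restore 90% in any setting examined, so it improves the fallback without making it a substitute for the paired comparison.

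These sizes rest on 1:1 allocation, 20 analysed subjects, equal variances in the two modes, and correlations that the documents do not give.

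**What to change.** In SAP 7.9.1.5 and protocol 12.4.1, state that any Period A-only treatment estimate will come from an ANCOVA of Visit 2 TEED on randomised first treatment, with Visit 1 cDBS TEED as covariate, and that it will be labelled supportive.

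Define the covariate from cDBS epochs only. Where timeline data before Visit 1 are short, use the programmed cDBS settings in the Visit 1 upload. Have SAP Appendix A state that the window before Visit 1 is delivered.

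While editing, reconcile the 0.10 and 0.15 pretest levels, since they govern when this estimate appears.

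The cost is a few sentences in each document, one degree of freedom, and a small model separate from the planned crossover model. No new visit or measurement is needed, but the Visit 1 TEED must be derived with care, and programmed current is a different source from the timeline average used for Period A. If the baseline correlation is near zero, a small amount of power is lost.

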7.9.1.6 Handling of missing data

All attempts will be made to minimize missing data. If missing data are observed, no imputation will be used for this analysis.

7.9.2 Secondary Objective

The secondary objective is to demonstrate maintenance within an optimal beta LFP threshold of beta LFP power during aDBS mode compared to cDBS. This objective will be assessed on the CC set.

7.9.2.1 Endpoint definition

The secondary endpoint is the mean percent time within an optimal beta LFP threshold of beta LFP power during aDBS mode compared to cDBS. The optimal beta LFP threshold indicates values between upper and lower LFP threshold preset for each patient.

7.9.2.2 Hypothesis

The formal hypothesis testing is:

$$H_0: \mu LFP_{aDBS} - \mu LFP_{cDBS} = 0 \quad \text{vs.} \quad H_a: \mu LFP_{aDBS} - \mu LFP_{cDBS} \neq 0,$$

where the difference ($\mu LFP_{aDBS} - \mu LFP_{cDBS}$) is the mean LFP change.

7.9.2.3 Analysis methods

The secondary endpoint will be assessed based on data collected from the Percept device using Brain Sense Timeline View function. Denote the LPF on aDBS by LFP_{aDBS} and the corresponding value for cDBS by LFP_{cDBS} . For each patient the difference between LFP_{aDBS} and LFP_{cDBS} will be calculated ($LFP_{aDBS} - LFP_{cDBS} = LFP_{DIFF}$). The mean percent time within an optimal threshold calculation will be provided by Rune Labs according to the Appendix A. The endpoint will be analyzed using a Paired T-test or nonparametric Wilcoxon Rank-Sum Test according the LFP normal or non-normal distribution between percent of time in the window for the preferred aDBS mode vs cDBS.

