9.7 Randomization and Treatment Assignment

7 days or more after cDBS has been set and within 30 days after the baseline visit.

Subjects will be randomly assigned during a randomization to a subjects' preferred aDBS mode (single or dual threshold) or cDBS (BrainSense setting is ON). The randomization method is Permuted Block Randomization. The site personnel will obtain the randomization assignment via Remote Data Capture (RDC). The randomization assignment can be obtained upon completion of the Informed Consent, Inclusion/Exclusion Criteria and randomization CRFs.

Crossover is performed after 45 (± 7) days when a preferred aDBS mode (single or dual threshold) or cDBS is assigned to a subject. A subject will not have knowledge of the DBS mode assigned for the duration of the aDBS treatment phase.

The PI/Sub investigator explains to the subjects that the assigned DBS mode cannot be changed except in an emergency. If it is necessary to adjust the stimulation mode the patient needs to return to the study site to make adjustments. Visits for adjustments are recorded as unscheduled visits. All adjustments must be completed at least 14 days prior to the next visit. Any adjustments should be recorded as unscheduled visits. Any adjustments during the 14 days prior to the next visit will be considered as a protocol deviation.

In order to blind the subject to the aDBS mode assigned, PI/Sub investigator will set the group name of the preferred aDBS mode to "DBS1," the group name of cDBS to "DBS2" and the group name of non-adjusted or the non-preferred aDBS mode to "DBS3" on the Clinician Programmer. If there is another mode that has already been set, set the group name to "DBS4". These group names will be displayed on the Patient Programmer.

If blinding is broken during the aDBS treatment phase, record the reason for the blind breaking in the medical records of the subject and report it as a deviation.

9.8 aDBS Treatment Phase

This phase consists of three treatment periods [Period A initiation (Visit 1), Post Period A (Visit 2) and Post Period B (Visit 3)].

For subjects implanted a directional lead with separate electrodes (e.g., SenSight), set the output of each separate electrodes uniformly (use it as a ring-shaped electrode).

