11.8 Product Complaint Reporting

Product complaint reporting and vigilance reporting are applicable and DDs and AEs related to any market released device during the study must be reported. The reporting of product complaints except for all reportable AE information for this study is not part of the study and should be done in addition to the AE reporting requirements. Refer to local regulations for reporting requirements.

Product Complaint: Any written, electronic or oral communication that alleges deficiencies related to the identity, quality, durability, reliability, safety, effectiveness or performance of a medical device that has been placed on the market.

It is the responsibility of the PI/ Sub investigator to report all product complaint(s) associated with a

medical device distributed by Medtronic, regardless whether they are related to intended use, misuse or abuse of the product. Reporting must be done immediately and via the regular channels for market-released products. Medtronic will notify the Ras (e.g. CA) as applicable in accordance with the requirements upon learning of them and is not limited to AEs and DDs only.

12. Statistical Design and Methods

The study participants will be randomized to either sequence: the first treatment is aDBS and then cDBS, or the first treatment is cDBS then aDBS. According to the randomized sequence, the first treatment DBS mode is started in Period A and second DBS mode is started in Period B. Supporting analyses for the primary objective include verifying the lack of a period or carryover effect in randomized subjects.

The Early Adapter Part II study will be considered successful when the primary objective of the study is met. The main analysis of primary and secondary objectives will use the Complete Case set (CC) which include all subjects who initiate the aDBS treatment phase and have complete data for the respective analysis. The main analysis will include data from all sites. An assessment for poolability of the results across clinical sites will be conducted by descriptive analyses for individual sites for the primary and key secondary endpoint. Subject disposition will be reported in a CONSORT diagram to show the flow of participants through stages of the study.

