12.5.1. Secondary Objective #1

The secondary objective is to demonstrate maintenance within an optimal beta LFP threshold of beta LFP power during aDBS mode compared to cDBS.

The formal hypothesis testing is:

$$H_0: \mu_{\text{LFPaDBS}} = \mu_{\text{LFPcDBS}}$$

$$H_a: \mu_{\text{LFPaDBS}} \neq \mu_{\text{LFPcDBS}}$$

The secondary endpoint is the mean percent time within an optimal beta LFP threshold of beta LFP power during aDBS mode compared to cDBS. The optimal beta LFP threshold indicates values between upper and lower LFP threshold preset for each patient.

The secondary endpoint will be assessed based on data collected from the Percept device using Brain Sense Timeline View function and will be analyzed using a Paired T-test or nonparametric Wilcoxon Rank-Sum Test according the LFP normal or non normal distribution between percent of time in the window for the preferred aDBS mode vs cDBS.

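### The gatekept secondary endpoint is tested by a paired t-test that ignores period and sequence, with no inferential period check, adjustment or fallback planned for it

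*SAP*

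**What the plan says.** - **Design.** The opening of protocol section 12 states "The study participants will be randomized to either sequence: the first treatment is aDBS and then cDBS", or the reverse order. Protocol 9.7 adds "The randomization method is Permuted Block Randomization", without a ratio or block size.
- **Secondary test.** Protocol 12.5.1 says the endpoint "will be analyzed using a Paired T-test or nonparametric Wilcoxon Rank-Sum Test". SAP 7.9.2.3 forms each patient's aDBS minus cDBS difference and says "The endpoint will be analyzed using a Paired T-test" or the same rank test. No period or sequence term appears. Protocol 12.5 places this test behind the primary as gatekeeper, at two-sided 0.05.
- **Analysis set.** The secondary uses the complete-case set without imputation (SAP 7.9.2 and 7.9.2.4). The SAP set also requires bilateral aDBS (7.1.3), and SAP section 6 expects about 25% of subjects to be excluded as unilateral.
- **Period checks.** Protocol 12.4.1, under the primary objective, says "The analysis approach makes two main assumptions: no period effect and no carryover effect". It tests these at 0.10 and otherwise allows period A data alone. SAP 7.9.1.5 fits a two-period crossover model to average TEED, at 0.15, with an optional first-period comparison. Protocol 12.5.1 and SAP 7.9.2 have no counterpart.
- **Descriptives.** SAP 7.2 promises summary statistics for each randomisation group and period.

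**The concern.** In a two-sequence crossover, a change from Period A to Period B that affects everyone enters the aDBS minus cDBS difference with a negative sign in the aDBS-first sequence and a positive sign in the cDBS-first sequence. A test that pools the differences treats this systematic split as random noise. If the two sequences contribute unequal numbers, the split no longer cancels, and part of a time trend is credited to a treatment.

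Some drift is conceivable for this endpoint. Percent time is scored against thresholds preset for each patient, at baseline or before the study. Stimulation adjustments are allowed up to 14 days before a visit (protocol 9.7), and clinically necessary changes to PD medication are permitted (protocol 9.3). At stake are power and, with unequal sequences, the accuracy of the estimate for the only other endpoint with a formal test.

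**Working it through.** **Inputs.** Protocol 12.8: N = 20, difference 22, SD of the paired difference 28, two-sided 0.05. These are TEED figures. They are used here because no planning figure exists for percent time, so results should be read in SD units. Assumed: 1:1 allocation, and a shared drift π (Period B minus Period A) of 0.25, 0.5 or 1.0 SD, that is 7, 14 or 28 units.

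**Plan's own figure.** 22/28 = 0.786. The noncentrality is 22/(28/√20) = 3.514 with 19 df, giving power of 91.5%. The smallest N for 90% is 20, so the stated figure reproduces.

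**Model.** The mean difference is τ − π in the aDBS-first sequence (n1) and τ + π in the cDBS-first sequence (n2), with N = n1 + n2.

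- Paired t-test: bias = π(n2 − n1)/N; expected sample variance = σ² + 4π²n1n2/[N(N − 1)].
- Period-adjusted: the mean of the two sequence means, which is unbiased for τ; SE = (σ/2)√(1/n1 + 1/n2), with N − 2 df.

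**Balanced, 10:10.** Bias is 0. At π = 14 the variance is 784 + 4·196·100/380 = 990.3, so the SD rises from 28 to 31.5. At π = 7 it is 28.9. Rejection rates are from 100,000 simulated trials per cell:

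| Drift | Paired t power | Adjusted power | Paired t type I error |
|---|---|---|---|
| 0.25 SD | 90.4% | 91.3% | 4.2% |
| 0.5 SD | 86.8% | 91.3% | 2.8% |
| 1.0 SD | 69.2% | 91.3% | 0.6% |

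**Unequal sequences, drift opposing the effect.**

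| Split, drift | Size of bias | Paired t power | Adjusted power | Paired t type I error |
|---|---|---|---|---|
| 12:8, 0.25 SD | 1.4 | 86.3% | 90.2% | 4.7% |
| 12:8, 0.5 SD | 2.8 (0.1 SD) | 76.1% | 90.2% | 4.4% |
| 13:7, 0.25 SD | 2.1 | 84.2% | 88.7% | 5.5% |
| 13:7, 0.5 SD | 4.2 (0.15 SD) | 69.4% | 88.7% | 6.5% |

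If the drift runs the other way, the same bias flatters the effect. At 14:6, type I error of the paired t-test is about 6.4%, 9.7% and 13.4% at 0.25, 0.5 and 0.75 SD. The adjusted test stays near 5% throughout.

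**How likely are such splits?** The least favourable case within the planned 20-30 is 30 randomised 15:15 with 10 lost at random. The chance of k aDBS-first subjects among the 20 analysed is C(15,k)·C(15,20−k)/C(30,20), with C(30,20) = 30,045,015.

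- 12:8 or worse: 1 − (2·5005·1365 + 3003²)/30,045,015 = 24.5%.
- 13:7 or worse: 2(105·6435 + 15·5005 + 3003)/30,045,015 = 5.0%.
- 14:6 or worse: 2(15·5005 + 3003)/30,045,015 = 0.5%. With 26 or fewer randomised it cannot occur, since neither sequence then has 14 subjects.

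**Price of adjusting when there is no drift.** Adjusted noncentralities are 22/6.261 = 3.514 (10:10), 22/6.390 = 3.443 (12:8), 22/6.563 = 3.352 (13:7) and 22/6.831 = 3.220 (14:6), each with 18 df. Power is 91.3%, 90.2%, 88.7% and 86.1%, against 91.5% unadjusted. The loss is about 0.2, 1, 3 and 5 points.

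**The case against.** **Drift is assumed, not shown.** This stands. Inclusion criterion 6 and protocol 9.3 call for stable PD medication through the treatment phase. SAP Appendix A uses only the two weeks before each visit, so the two windows lie about 45 days apart. No drift, SD or effect is given for percent time.

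**The plan does look at period.** SAP 7.2 would show means by randomisation group and period. That could reveal a shift, but it is descriptive and changes neither the test nor the estimate.

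**False positives are not a realistic worry.** Largely right. With balanced sequences the test is conservative, and at 12:8 it still holds 5%. Inflation needs both drift and a split of 13:7 or worse. The preferred aDBS mode is determined before randomisation. If unilateral or bilateral status is fixed then too, the bilateral-only exclusion is unrelated to sequence. Only sequence-related loss would make large imbalance likely, and the documents give no reason to expect it.

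**The primary is covered.** A reader might infer that TEED has the same open gap, because SAP 7.9.1.4 says "The primary endpoint on the difference in TEED will be assessed by means paired t-test". The documents do not support that: the no-period and no-carryover assumptions are stated, tested, and given a first-period fallback. The safeguard is partial. At 10:10 it detects a 0.25 SD drift in only 29% (0.10 level) to 37% (0.15 level) of trials, and the two thresholds conflict. But it exists.

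**Consequences are limited.** Also true: study success rests on the primary alone, and no power is claimed for the secondary.

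**Conclusion.** The point holds for the secondary endpoint. A randomised crossover is analysed as simple paired data, and nothing inferential protects this test from a shared time shift.

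The size is modest and conditional. At the TEED effect size, balanced sequences lose about 1 power point at a 0.25 SD drift and 4 to 5 at 0.5 SD, without bias. A 12:8 split is quite possible if many of those randomised are not analysed. With a 0.5 SD drift it brings a 0.1 SD bias and, if that opposes the effect, 76% rather than 90% power. Type I error passes 5% only at about 13:7 or worse, and 14:6 is an extreme case under 1:1 blocks with random loss. All of this rests on an assumed drift and a borrowed effect size.

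It would be wrong to conclude that the secondary result will be biased, that its error rate is badly inflated, or that any drift in TEED goes unaddressed. The case for change is that the correct estimator is standard, uses data already collected and costs little when sequences are near balance.

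**What to change.** In SAP 7.9.2.3 and protocol 12.5.1, make the main secondary analysis the period-adjusted crossover estimator: compare within-subject Period A minus Period B differences between the two randomised sequences by a two-sample t-test and halve the estimate. A model with subject, period and treatment is equivalent. Report the estimate with its 95% CI and the number of complete cases by sequence. For non-normal data, apply the rank-sum test to those same period differences between sequences. Keep the paired t-test as a sensitivity analysis.

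No new data are needed, and SAP 7.9.1.5 already plans a two-period crossover model for TEED. The cost is one degree of freedom plus the loss of efficiency under imbalance: with no drift, about 0.2 power points at 10:10, 1 at 12:8, 3 at 13:7 and 5 at 14:6. The estimator removes an additive shift common to both sequences; it does not deal with carryover.

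Using the same estimator for TEED in SAP 7.9.1.4 and protocol 12.4 would be an optional change for consistency.
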